12.0 Background

12.1 Background:

Ischemic heart disease (IHD) is the leading cause of death in Veterans and has been identified as a priority condition for improving healthcare within the VA. Exercise-based cardiac rehabilitation (CR) is an evidence-based, cost effective therapy that reduces morbidity and mortality following acute myocardial infarction (MI), coronary artery bypass grafting (CABG) or percutaneous coronary intervention (PCI). The American Heart Association (AHA) and American College of Cardiology (ACC) recommend referral to CR as one of its 9 performance measures for secondary prevention (along with aspirin, beta blockers, statins and smoking cessation) in patients with IHD. Unfortunately, despite the compelling benefits and widespread endorsement of its use, CR is vastly underutilized in VHA. A recent Presidential Advisory from the AHA concluded, "The remarkably wide treatment gap between scientific evidence of the benefits of cardiac rehabilitation and clinical implementation is unacceptable." Only 35 (27%) of VA facilities offer CR programs, and less than 10% of eligible veterans receive this guideline-recommended therapy. Geographic distance is by far the largest barrier to participation. Of the 9.2 million veterans currently enrolled in VHA, 6.7 million (73%) live more than 60 minutes from a VA CR center [based on geography data from VA Planning Systems Support Group (PSSG)]. Thus, there is an urgent need to adapt CR programs to improve access to and utilization of CR among rural veterans.

12.2 Preliminary studies:

In a recent study conducted at the Iowa City VA (Wakefield et al, 2014), 48 patients completed a home-based program and 12 patients completed face-to-face CR. There was no difference in blood pressure, lipid levels, weight, glycosylated hemoglobin or rate of rehospitalization between the two groups. Home-based CR participants were highly satisfied with their care and had a better completion rate than patients who underwent face-to-face CR (89% vs. 73%). Costs for home and center-based CR programs were comparable. These findings suggest that a home-based CR program is a viable, safe, and cost- effective alternative to center-based programs. In a 2010 Cochrane review, there was no significant difference in mortality among patients randomly assigned to home-based CR vs. center-based CR.

12.3 References:

If you have a separate bibliography, attach it to the submission with your other study documents.

13.0 Sample Size and Eligibility

13.1 Number of subjects that will be enrolled at UCSF and affiliated institutions:

200

13.2 Total number of subjects that will be enrolled at all sites (Help Text updated 9/13):

400

13.3 Estimated number of people that you will need to consent and screen here (but not necessarily enroll) to get the needed subjects:

400

13.4 Explain how and why the number of subjects was chosen (Help Text updated 9/13):

Sample size estimation for the difference between two groups over four assessments assuming a linear trend. The estimate is based on a two-sided alpha of .05, power of .90, a constant correlation of 0.5 among all repeated measurements, and a 5% overall attrition. San Francisco will enroll 200 participants while the other centers will enroll 100 participants each with a study total of 400 participants. With these assumptions, a composite effect of .5 can be detected

13.5 * Eligible age range(s):

- 0-6 years
- 7-12 years
- 13-17 years
- 18+ years

13.6 Inclusion criteria:

- CABG within 6 months prior to first session
- PCI within 6 months prior to first session
- Acute MI within 6 months prior to first session

13.7 Exclusion criteria:

- Age < 18 years
- Pregnant
- Behavioral or cognitive limitations that interfere with performing exercise training
- Significant movement disorder that interferes with exercise training
- Blind, deaf or mute
- Homeless (or unstable housing anticipated during the next 3 months)
- LVEF <35% without ICD
- Staged PCI with significant remaining lesion
- Decompensated heart failure
- QTc > 500 msec and no ICD
- 6MWT < 75 m (post-op) or < 150 m (non-surgical)
- Long-term (>30 days) SNF placement
- Atrial arrhythmia not rate controlled
- Mobitz Type II or 3rd degree AV block without pacemaker
- Deceased
- History of unprovoked or exercise-induced VT, VF or syncope with no ICD
- Concerning ventricular ectopy in past 24 hours with no ICD (Lown grading system)
 - Polymorphic/multiform PVCs
 - Couplets, Salvos, or non-sustained VT
 - R on T pattern
 - >10 PVCs per minute

13.8 There are inclusion or exclusion criteria based on gender, race or ethnicity:

Yes No

If **yes**, please explain the nature and rationale for the restrictions:

14.0 Other Approvals and Registrations**14.1 * Do any study activities take place on patient care units:**

Yes No

If **Yes**, attach a letter of support for the study from the involved patient care manager(s).

14.2 * Does your protocol involve any radiation exposure to patients/subjects? The UCSF Radiation Safety Committee requires review of your protocol if it includes administration of radiation as part of standard of care OR research exposures:

Yes No

14.3 * This study may generate genetic data that may be broadly shared (e.g. submitted to NIH for Genome-Wide Association Studies (GWAS) in dbGaP, TCGA, etc):

Yes No

14.4 * This study involves administration of vaccines produced using recombinant DNA technologies to human subjects:

Yes No

14.5 * This study involves human gene transfer (NOTE: Requires NIH Recombinant DNA Advisory Committee (RAC) review prior to CHR approval):

Yes No

14.6 This study involves other regulated materials and requires approval and/or authorization from the following regulatory committees:

Institutional Biological Safety Committee (IBC)

Specify BUA #:

Institutional Animal Care and Use Committee (IACUC)

Specify IACUC #:

Radiation Safety Committee

Specify RUA #:

Radioactive Drug Research Committee (RDRC)

Specify RDRC #:

Controlled Substances

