The only difference between the sites is that San Francisco offers a home-based cardiac rehab program and other sites will offer a center-based cardiac rehab program. Research outcomes will include processes of care (% of eligible patients referred, % enrolled, average number of sessions completed, provider knowledge) and patient outcomes (6 minute walk distance, physical activity, quality of life, patient and caregiver satisfaction, rehospitalization, mortality). The study will evaluate the effectiveness of each CR program on these outcomes. In addition, research participants will be asked to participate in a total of 3 additional study visits. The visits will take place 3 months, 6 months, and 12 months after their enrollment in the cardiac rehabilitation program. Medical records will be reviewed and death certificates will be obtained for up to 10 years of follow-up.

Statistical Analysis Plan

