The outcomes listed will be measured at baseline, and then at 3, 6, and 12 months following first visit to CR. Prior to inferential statistics, we will use descriptive statistics and graphs to explore distributions, univariate outliers, and basic bivariate associations with home- vs. center-based CR. We will then compare baseline characteristics of the two groups to examine differences on key subgroup variables including age and type of procedure resulting in the need for CR. Imbalanced baseline measures will be included as covariates in outcome analyses. To appropriately model these nested data, we will use linear mixed models also called multilevel or hierarchical linear models. Our primary outcomes on which only the patient or their caregiver provide data will be analyzed using a multivariate regression model with a simple random -effects structure with repeated-measures. We anticipate that patients who agree to enroll in home-based CR will be different than those who agree to enroll in center- based CR. Therefore, we will use other variables measured at baseline to construct a propensity score for home- vs. center-based CR, and we will adjust the multivariable analyses for this propensity score. Planned subgroup analyses will include the effects of the following predictors on outcomes: age, gender, race/ethnicity, SES, distance to nearest facility that can provide rehabilitation, and presence of caregivers. We will determine whether these same socio-demographic factors are associated with patient preference. We will also conduct subgroup analyses where we have identical measures from patients and caregivers.

Study Application (Version 1.14)

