In addition, research participants will be asked to participate in a total of 2 additional study visits. The visits will take place 3 months and 6 months after their enrollment in the cardiac rehabilitation program. Medical records will be reviewed and death certificates will be obtained for up to 10 years of follow-up. This protocol will require national access to VA electronic health records through CAPRI and/or VistAWeb.

10.2 If this is a clinical trial, check the applicable phase(s) (Help Text updated 9/13):

- Phase I
- Phase II
- Phase III
- Phase IV

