11.0 Scientific Considerations

11.1 Hypothesis (Help Text updated 9/13):

This study has a hypothesis:

Yes No

If yes, state the hypothesis or hypotheses:

Patients undergoing home based cardiac rehabilitation will not differ in 6 minute walk time, physical activity, quality of life, patient and caregiver satisfaction, and re-hospitalization as compared with patients undergoing center-based cardiac rehabilitation.

11.2 * List the specific aims:

Aim 1. Determine whether automatic referral to home- vs. center-based CR increases patient participation in CR after hospitalization for myocardial infarction or coronary revascularization.

Aim 2. Among patients who choose to participate in CR, compare the effectiveness of home- vs. center-based CR on six-minute walk distance, quality of life, and healthcare expenditures.

Aim 3: Determine whether the effects of home vs. center-based CR differ by age, gender, race, ethnicity, distance from medical center, employment, socioeconomic status, social support, caregiver status, comorbid conditions, or patient preference.

11.3 Statistical analysis:

The outcomes listed will be measured at baseline, and then at 3 and 6 months following first visit to CR. Prior to inferential statistics, we will use descriptive statistics and graphs to explore distributions, univariate outliers, and basic bivariate associations with home- vs. center-based CR. We will then compare baseline characteristics of the two groups to examine differences on key subgroup variables including age and type of procedure resulting in the need for CR. Imbalanced baseline measures will be included as covariates in outcome analyses.

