- Extremely active (5 or more times/week)

X X X

Typical week during the past month

Frequency **I**ntensity **T**ime

Type

X X X

Number of hours sitting per weekday

X X X

Overall quality of life

X X X

Disease-specific quality of life

X X X

Depressive symptoms

X X X

Anxiety symptoms

X X X

Positive affect

X X X

Servings fruits/vegetables per day

X X X

Smoking

X X X

Alcohol use

X X X

Drug use

X X X

Comorbid medical conditions

X X X

The following table lists all information collected from study subjects for research only. This includes information collected from subject interviews, questionnaires, and other research activities (i.e. the six minute walk test conducted at months 3 and 6). The table also includes the timepoint at which the information is collected.

	Baseline	12 weeks	6 months
Measurements			
6MWT standardized course			
Date	SOC	X	X
Start time (_ : _)	SOC	X	X
End time (_ : _)	SOC	X	X
Total distance (meters? feet?)	SOC	X	X
Peak heart rate	SOC	X	X
O ₂ sat at end of course	SOC	X	X
Max perceived exertion (Borg 1-10)	SOC	X	X
Comments	SOC	X	X
Trails A and B (seconds to complete)	X	X	
Digit symbol (# correct in 120 sec)	X		X
Number of chair stands in 30 sec	X		X
Overall quality of life	X	X	X
Disease-specific quality of life	X	X	X

Satisfaction with health care	X	X	X
Sleep quality	X	X	X
Positive affect	X	X	X
Caregiver communication	X	X	X
Functional status (ADLs, IADLs)	X	X	X
Cardiac self-efficacy	X	X	X
Exercise self-efficacy	X	X	X
Patient Activation	X	X	X
Rate My Plate	X	X	X
Servings fruits/vegetables per day	X	X	X
Grams of saturated fat per day	X	X	X
Medication adherance	X	X	X
Smoking	X	X	X
Other Outcomes			
Days until resume driving		X	
Days until resume intercourse		X	
Days until resume work		X	
Patient (out of pocket) expenses		X	
Knowledge about cardiac disease	X	X	X
Days until rehospitalization	X	X	X
Reason for rehospitalization	X	X	X
Days until death	X	X	X
Cause of death	X	X	X
Tandem Stand Test	X	X	X
Side by side Stand Test	X	X	X
Heel Toe Stand Test	X	X	X

If you have a procedure table, attach it to the submission with your other study documents.

15.2 Interviews, questionnaires, and/or surveys will be administered or focus groups will be conducted:

Yes No

List any standard instruments used for this study:

Trails A and B cognitive function tests
 Digit symbol cognitive function test
 Seattle Angina Questionnaire
 Patient Activation Measure
 International Physical Activity Questionnaire

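### The sample size and the SAP rest on four assessments including month 12, but the application schedules only baseline, 3 and 6 months

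*Combined protocol and SAP*

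**What the plan says.** **Four assessments.** Section 13.4 reads "Sample size estimation for the difference between two groups over four assessments assuming a linear trend". Its inputs are two-sided alpha .05, power .90, a constant correlation of .5 and 5% attrition, with 200 participants in San Francisco and 400 in total. It ends: "With these assumptions, a composite effect of .5 can be detected". The Study Design section of the front protocol says that "research participants will be asked to participate in a total of 3 additional study visits", at 3, 6 and 12 months. The Statistical Analysis Plan says: "The outcomes listed will be measured at baseline, and then at 3, 6, and 12 months following first visit to CR".

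**Three assessments.** Section 10.1 says that "research participants will be asked to participate in a total of 2 additional study visits", at 3 and 6 months. Section 11.3, which otherwise repeats the SAP text, says: "The outcomes listed will be measured at baseline, and then at 3 and 6 months following first visit to CR". Both tables in 15.1 have columns for baseline, 12 weeks and 6 months only, and the text there refers to "the six minute walk test conducted at months 3 and 6". Section 15.6 totals about 4 hours over 6 months. Section 24.2 lists three payments, the last for the 6-month assessment.

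The only later follow-up in the application is passive: "Medical records will be reviewed and death certificates will be obtained for up to 10 years of follow-up".

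**The concern.** The number and timing of assessments determine the endpoint, the repeated-measures model and the sample-size calculation. Here the calculation and the SAP use one schedule and the operational sections use another. The conflict does not depend on the front matter: 13.4 contradicts 10.1, 11.3, 15.1, 15.6 and 24.2 within the same application.

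Two things are at stake. First, if the operational sections stand, the SAP's 12-month results for six-minute walk, quality of life, activity and satisfaction will not exist, and a visit that was never held cannot be recovered later. Rehospitalization and mortality at 12 months could still come from records and death certificates. Second, the justification given for 400 participants would not describe the data to be analysed. Because 13.4 gives a count of assessments without months, and an effect without unit or visit, a reader cannot tell whether losing one assessment matters little or a lot.

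**Working it through.** **1. Schedules side by side**

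| Place | Assessments |
|---|---|
| Front protocol, Study Design | 3 additional visits: 3, 6, 12 months |
| SAP | baseline, 3, 6, 12 months |
| 13.4 | four, months not given |
| 10.1 | 2 additional visits: 3, 6 months |
| 11.3 | baseline, 3, 6 months |
| 15.1, both tables | baseline, 12 weeks, 6 months |
| 15.6 | 1 + 1.5 + 1.5 = 4 hours, over 6 months |
| 24.2 | 3 × $50 = $150 |

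The totals in 15.6 and 24.2 add up only for three assessments. A fourth on the same terms would give 5.5 hours and $200.

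**2. Model for the power check**

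Inputs from 13.4: two-sided alpha .05, power .90, correlation .5, 5% attrition, 200 per arm, so 200 × .95 = 190 analysed per arm. Assumed, because 13.4 does not say: the test is of a difference in linear slopes, variances are equal over time, and the effect is in SD units.

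- Variance of the slope difference = 2(1 − .5)/(Sxx × n) = 1/(Sxx × n), where Sxx is the sum of squared deviations of the visit times from their mean.
- n per arm = (1.960 + 1.282)² / (Sxx × slope²) = 10.507/(Sxx × slope²).
- Power = Φ(slope × √(Sxx × n) − 1.960).
- Sxx: times 0, 3, 6, 12 give 78.75; 0, 3, 6 give 18; 0, 1, 2, 3 give 5; 0, 1, 2 give 2.

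**3. The plan's own figure, four assessments, .5 SD reached at the last visit**

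- Times 0, 3, 6, 12: 10.507/(78.75 × (.5/12)²) = 76.9, so 77 per arm; 77/.95 gives 82 enrolled per arm, 164 in total.
- Equal spacing: 10.507/(5 × (.5/3)²) = 75.7, so 76 per arm; 76/.95 = 80 enrolled per arm, 160 in total.
- Power at 190 per arm is .999 in both cases.

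The stated 400 is not reproduced. A time-averaged effect over four assessments (53 per arm) and a plain comparison of two means (85 per arm) do not reproduce it either.

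**4. Three assessments, 190 analysed per arm**

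| Reading of .5 | Slope | Sxx | Power | n per arm for .90 |
|---|---|---|---|---|
| .5 SD at 12 months, so .25 SD at 6 months | .5/12 per month | 18 | .683 | 336.2, so 337 (355 enrolled) |
| .5 SD at the fourth of four equally spaced visits | .5/3 per visit | 2 | .901 | 189.1, so 190 (200 enrolled) |
| .5 SD at 6 months | .5/6 per month | 18 | .998 | 84.1, so 85 (90 enrolled) |

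**5. Detectable difference at .90 power, 190 per arm, whichever reading applies**

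- Times 0, 3, 6: slope 3.242/√(18 × 190) = .0554 SD per month; × 6 = .333 SD at 6 months.
- Times 0, 3, 6, 12: slope 3.242/√(78.75 × 190) = .0265 SD per month; × 12 = .318 SD at 12 months.

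**The case against.** The strongest reply is that no loss of power is shown. The detectable differences at the last visit, .333 and .318 SD, are almost equal. The .68 arises only if .5 SD is a 12-month target, so that the 6-month target is .25 SD. Under that reading four visits would give .999 and need 164 participants, which fits neither the stated .90 nor the 400. One three-visit reading does match the plan: with a slope of .5/3 per visit, 190 analysed per arm and 5% attrition give 200 per arm and 400 in total. All of this stands. The match may be coincidence, and it does not remove the word four from 13.4, but 400 cannot be called unsupported for three visits.

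A second reply is that the application is partly local. Section 15.7 places all activities at San Francisco or by telephone, and the other sites' visit and payment schedules are not in these documents. That is true. But San Francisco supplies the whole home-based arm, so without a 12-month visit there no 12-month comparison of walk distance is possible.

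A third reply is that follow-up of up to 10 years covers month 12. It covers rehospitalization and death only. Records and death certificates do not yield a scheduled walk test or study questionnaires.

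**Conclusion.** The concern holds. Current text gives two incompatible schedules, and nothing in the documents reconciles them. The sample-size basis in 13.4 and the 12-month outcomes in the SAP are not delivered by the application's operational sections.

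The certain consequence is the absence of 12-month visit-based outcomes if those sections stand. The consequence for power is indeterminate: about .68, .90 or above .99 with three visits, under the assumed slope model with equal variances and effects in SD units. Since that model with four visits calls for only 160 to 164 participants, it is not evidently the sponsor's method. The range should be read as showing that the .5 is undefined, not that the study is underpowered.

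**What to change.** Choose one assessment schedule and apply it throughout. In either case, state in 13.4 the months of assessment, the unit of the .5 effect and the visit to which it applies.

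- **If three assessments stand:** remove the 12-month visit from the front protocol and the 12-month visit-based outcomes from the SAP. Recalculate and restate in 13.4 the power or detectable effect for baseline, 3 and 6 months with 400 participants. The cost is text edits and one figure. The 12-month visit-based claims are lost, and the restated power may be less favourable.
- **If four stand:** carry the 12-month assessment into 10.1, 11.3, 15.1, 15.6 and 24.2. The cost is one more visit per participant with its staff time and payment, an application modification, and notice to the other sites through the study memoranda described in 8.1.

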Test the hypothesis that patients undergoing home based cardiac rehabilitation will not differ in 6 minute walk time, physical activity, quality of life, patient and caregiver satisfaction, and re-hospitalization as compared with patients undergoing center-based cardiac rehabilitation.

Aim 1. Determine whether automatic referral to home- vs. center-based CR increases patient participation in CR after hospitalization for myocardial infarction or coronary revascularization.

Aim 2. Among patients who choose to participate in CR, compare the effectiveness of home- vs. center-based CR on six-minute walk distance, quality of life, and healthcare expenditures.

Aim 3: Determine whether the effects of home vs. center-based CR differ by age, gender, race, ethnicity, distance from medical center, employment, socioeconomic status, social support, caregiver status, comorbid conditions, or patient preference.

Study Design

Cardiac rehabilitation involves exercise training, education, and lifestyle counseling for patients with cardiac conditions. Home and center-based cardiac rehabilitation programs, if followed by patients, are equally effective in their benefits on risk factors, health-related quality of life, death, and clinical events following acute myocardial infarction or coronary revascularization. This study will compare the effectiveness of existing cardiac rehabilitation programs. The San Francisco VA Medical center offers a home-based (but not a center based) cardiac rehabilitation program to patients who are hospitalized for myocardial infarction, percutaneous coronary intervention, or coronary artery bypass grafting. The other study sites offer a center-based (but not a home-based) cardiac rehabilitation to the same group of patients. All facilities have initiated a comprehensive CR intervention with 7 components:

1. Educate and engage stakeholders (grand rounds, posters, brochures, one-on-one meetings)
2. Automate referrals

3. Standardize templates and stop codes for consults, progress notes, exercise prescription, and the patients' Individualized Treatment Plans
4. Use database to track all patients referred; monitor % enrolled, number of sessions completed.
5. Standardize outcome assessment
6. For CABG patients, provide in-hospital assessment and phase I cardiac rehabilitation; coordinate care with home PT
7. Offer a phase II cardiac rehabilitation program within 6 months of hospitalization.

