10.0 Study Design

10.1 * Study design (Help Text updated 9/13):

Cardiac rehabilitation involves exercise training, education, and lifestyle counseling for patients with cardiac conditions. Home and center-based cardiac rehabilitation programs, if followed by patients, are equally effective in their benefits on risk factors, health-related quality of life, death, and clinical events following acute myocardial infarction or coronary revascularization. This study will compare the effectiveness of existing cardiac rehabilitation programs. The San Francisco VA Medical center offers a home-based (but not a center-based) cardiac rehabilitation program to patients who are hospitalized for myocardial infarction, percutaneous coronary intervention, or coronary artery bypass grafting. The other study sites offer a center-based (but not a home-based) cardiac rehabilitation to the same group of patients. All facilities have initiated a comprehensive CR intervention with 7 components:

1. Educate and engage stakeholders (grand rounds, posters, brochures, one-on-one meetings)
1. Automate referrals
1. Standardize templates and stop codes for consults, progress notes, exercise prescription, and the patients' Individualized Treatment Plans
1. Use database to track all patients referred; monitor % enrolled, number of sessions completed.
1. Standardize outcome assessment
1. For CABG patients, provide in-hospital assessment and phase I cardiac rehabilitation; coordinate care with home PT
1. Offer a phase II cardiac rehabilitation program within 6 months of hospitalization.

The only difference between the sites is that San Francisco offers a home-based cardiac rehab program and other sites will offer a center-based cardiac rehab program.

Research outcomes will include processes of care (% of eligible patients referred, % enrolled, average number of sessions completed, provider knowledge) and patient outcomes (6 minute walk distance, physical activity, quality of life, patient and caregiver satisfaction, re-hospitalization, mortality). The study will evaluate the effectiveness of each CR program on these outcomes. All 6 minute walk tests associated with the home-based portion of the study will be conducted at the San Francisco VA Medical Center.

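### Rehabilitation type is fixed by site, with San Francisco as the whole home arm, so a home effect cannot be separated from a San Francisco effect and the planned intervals are too narrow for a general home-versus-center claim

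*Combined protocol and SAP*

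**What the plan says.** Both design descriptions (Study Protocol, Study Design; Study Application, 10.1) say that San Francisco runs a home program and no center program, and then: "The other study sites offer a center-based (but not a home-based) cardiac rehabilitation to the same group of patients". They add "The only difference between the sites is that San Francisco offers a home-based cardiac rehab program and other sites will offer a center-based" one. On shared practice, 10.1 says "All facilities have initiated a comprehensive CR intervention with 7 components".

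Section 13.4 describes its calculation as "Sample size estimation for the difference between two groups over four assessments assuming a linear trend". Its inputs are two-sided alpha .05, power .90, a constant within-patient correlation of .5, 5% attrition and a composite effect of .5. On allocation it says "San Francisco will enroll 200 participants while the other centers will enroll 100 participants each with a study total of 400 participants". That implies (400 − 200)/100 = 2 center sites, although the number is not stated.

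The Statistical Analysis Plan and 11.3 refer to nested data and multilevel models, but the only structure they describe is random effects for the repeated measurements. Adjustment is by imbalanced baseline covariates and a propensity score. Site is not named as a fixed effect, a random effect or a clustering level.

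Two targets of inference appear. The design text says "This study will compare the effectiveness of existing cardiac rehabilitation programs". The aims are general: Aim 1 is to "Determine whether automatic referral to home- vs. center-based CR increases patient participation in CR after hospitalization for myocardial infarction or coronary revascularization", and Aim 2 is to "compare the effectiveness of home- vs. center-based CR on six-minute walk distance, quality of life, and healthcare expenditures". Sections 17.4 and 17.5 also speak of home against center CR as such.

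**The concern.** With one home site, CR type is a function of site. Staffing, case mix, referral culture, measurement practice and local care at San Francisco all travel with the home label.

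The plan's safeguards reduce this problem but cannot remove it. The covariates and propensity score act on measured patient characteristics, and the seven shared components act on process. Adding site to the model does not help: a fixed site effect makes the home effect inestimable, and a random one on three sites leaves 1 degree of freedom. The assertion that CR type is the sole site difference cannot be tested with one home site.

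The hypothesis is that the groups do not differ, so a site difference can produce a false finding of no difference as easily as a false difference.

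The form of the outcome matters. On the linear-trend contrast a constant site shift cancels, and only site differences in change over time do harm. For participation, rehospitalization and expenditures there is no baseline level to subtract, so constant site differences stay in full.

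**Working it through.** **Inputs from 13.4.** 200 per group less 5% gives 190 analysable; one home site; two center sites (inferred) of 100, so 95 each after attrition; alpha .05 two-sided; correlation .5; effect .5 in SD units.

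**The plan's own figure.** With no site variance, an effect of .5 at .90 power needs the following per group (with attrition in brackets): 85 (90) at a single time point, 76 (80) for a linear divergence to .5 over four equally spaced visits, 53 (56) for the mean of four visits, 43 (46) for an orthonormal trend contrast. That is 92 to 180 in total, so 400 is not reproduced on these readings. No claim is made here about how it was derived. At patient level 400 is ample: the standard error (SE) is √(2/190) = .1026 and power for .5 is .998.

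**Assumed input.** The documents give no between-site variance. The range below is an assumption and means variance left after adjustment.

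**Single outcome or change score (SD 1).**

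- Var = ICC × (1/1 + 1/2) + (1 − ICC) × 2/190
- Type I error when site is ignored = 2Φ(−1.96 × .1026/SE)
- Power = Φ(.5/SE − 1.96), treating the site variance as known

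At ICC .01: Var = .0150 + .0104 = .0254, so SE = .1594.

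| ICC | SE | Type I error | Power for .5 | 95% half-width |
|---|---|---|---|---|
| 0 | .1026 | .05 | .998 | .20 |
| .005 | .1341 | .13 | .96 | .26 |
| .01 | .1594 | .21 | .88 | .31 |
| .02 | .2008 | .32 | .70 | .39 |
| .05 | .2915 | .49 | .40 | .57 |

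Power stays at or above .90 up to ICC of about .009. More patients at the same three sites cannot bring the SE below √(1.5 × ICC), which is .12 at ICC .01.

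**Linear-trend contrast.** The patient variance of slope × T is T² × .5/Sxx. At 0/3/6/12 months (Study Protocol schedule) Sxx = 78.75, giving 144 × .5/78.75 = .914. At 0/3/6 months (Study Application schedule) Sxx = 18, giving 36 × .5/18 = 1.000. Then Var = 2 × .914/190 + 1.5τ², where τ² is the site-by-time variance of the end-of-study difference in SD² units.

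| τ² | SE (0/3/6/12) | Type I error | Power for .5 | Detectable at .90 power |
|---|---|---|---|---|
| 0 | .0981 | .05 | .999 | .32 |
| .005 | .1309 | .14 | .97 | .42 |
| .01 | .1569 | .22 | .89 | .51 |
| .02 | .1991 | .33 | .71 | .64 |
| .05 | .2909 | .51 | .41 | .94 |

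At 0/3/6 months power at τ² .005/.01/.02/.05 is .96/.88/.70/.40. Simulation (400,000 runs, constant site variance .05 added) gave type I error .050/.142/.221/.335/.508 for the five rows. The first value confirms that a constant site shift does no harm on this contrast.

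**Estimating the site variance instead of assuming it.** With two center sites there is 1 degree of freedom and a critical t of 12.7. Simulated power for .5 is about .18/.15/.11 at ICC .01/.02/.05.

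**Aim 1 participation.** Site variance alone gives a 95% half-width of 1.96 × √(p(1−p) × 1.5 × ICC), however many patients are referred. With participation assumed at 30 to 50%, this is about 8, 11–12 and 25–27 points at ICC .005, .01 and .05. At 10%, near the national uptake ceiling quoted in the Background, it is about 5, 7 and 16 points.

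**By-site comparisons, patient-level error.** San Francisco against one center: 1.96 × √(1/190 + 1/95) = .25 SD. Center against center: 1.96 × √(2/95) = .28 SD. The center–center difference would reach p < .05 only 11%/16%/25%/41% of the time at ICC .005/.01/.02/.05, so it is a weak check on site variation.

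**The case against.** The best defence is that the study says it compares existing programs, and for that target patient-level errors are right. This stands as far as it goes. But the hypothesis, Aims 1 to 3 and sections 17.4 and 17.5 draw the general conclusion, and the plan never says which question its intervals answer.

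Second, the real defect is confounding, and the type I error figures treat the three sites as exchangeable draws with equal variance, which nothing in the documents supports. This is fair. The figures illustrate how much a modest site difference matters; they do not estimate it. Reusing the same numeric range for τ² as for the ICC is also a choice, so the two tables are not independent support.

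Third, the power figures assume a known site variance that three sites cannot supply. That is correct, and the 1-degree-of-freedom result shows the practical position is worse.

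Fourth, section 16.2 mentions referral from San Francisco to an outside center program, and 21.3 offers standard care whether or not a patient joins the study, so some crossover is conceivable. Section 16.2 describes that option for patients who decline the study, and no within-site comparison is planned. It does not break the link between site and CR type.

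**Conclusion.** The concern holds and should be fixed. CR type cannot be separated from site, and no allowance for site appears in 13.4 or the analysis plan. The planned intervals can support a statement about this home program against these center programs; they are too narrow for home versus center CR in general whenever residual site variance is above zero.

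A residual ICC of about .01 is enough to use up the patient-level surplus in the sample size and to make type I error roughly four times nominal (.21 against .05). These sizes rest on an assumed site variance, on two center sites inferred from the enrollment figures, and on site variance treated as known. For the trend contrast, the relevant quantity is site variation in change over time only.

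**What to change.** 1. In 13.4, state that the calculation assumes no between-site and no site-by-time variance and that CR type is fixed by site. Give power or the detectable effect at site (or site-by-time) variance 0, .005, .01, .02 and .05.
2. In 11.3 and the Statistical Analysis Plan, state that CR type cannot be separated from site. In both design sections, present the claim that sites differ only in CR type as an assumption.
3. Report San Francisco against each center separately beside the pooled result. Show the center–center difference as description only.
4. Add a sensitivity analysis restating the pooled 95% interval at site ICC 0, .005, .01, .02 and .05, with the half-widths tabulated above (the trend contrast gives about .19/.26/.31/.39/.57 SD).
5. Word all conclusions, including any claim of no difference, as this home program against these center programs.

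The cost is wording and a few tables from data already collected, with no added sites, patients or visits. The stated precision becomes less favourable and the claim narrower. The confounding itself is disclosed, not removed.
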